#### 8.5.2 Parental Satisfaction with ClaimIt Platform Questionnaire

Table 2a will describe the frequency and percent of "Yes" and "No" responses for Questions 2, 3, 5, 6, 7 and 8. For Question 5a, among subjects who indicated "Yes" for Question 5, the frequency and percent will be calculated for each reason of why there was scoring difficulty.

Tables 2b-2f represent the free text responses for Questions 2, 3, 4, 5, 8 of the questionnaire. Tables 2b-c and 2f (Questions 2, 3, and 8, respectively) represent responses among subjects who answered "Yes". Table 2d describes responses to Question 4, which is characterized as an open-ended question only. Table 2e includes responses from subjects who answered "Other" for Question 5a. The

number of subjects who completed the question and/or relevant sub-question will be listed within the table.

Table 3 represents the list of reasons for withdrawal from the study among subjects who dropped out prior to the study's conclusion. Figure 3 describes the number and percentage of subjects throughout the study process, beginning from the screening process to study completion (*see section 8.6*).

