APPENDIX V: Parental Satisfaction with ClaimIt Platform

The following questions are regarding the use of the ClaimIt application during your participation in this clinical trial:

1.	Please rate the ClaimIt application's overall ease of use on a scale of 1 to 5:
	(Very Difficult) 1 2 3 4 5 (Very Easy)
2.	Did the ClaimIt application malfunction?
	a. Yes (will be asked a follow-up question)
	b. No
	If Yes, please describe what happened:
	Tes, please describe what happened.
3.	Have you participated in any other clinical study?
	a. Yes (will be asked a follow-up question)
	b. No
	(If yes) What did you prefer about study participation using the ClaimIt application?
	Why?
	(If yes) What did you prefer about participation in the previous study? Why?
	·

Protocol V2 120CT2018

4.	Do yo	u have any comments about using the application (favorable or unfavorable) that
	you w	ould like the PIs to know?
		(Open ended question)
5.	•	ou find it difficult to score the stool pictures? Yes
	b.	No
	(If yes) Why?
	a.	Because the app was not easy to use to see the example pictures
	b.	Because it was not easy for me to score the stool, even with the example
		pictures provided
	c.	Because sometimes the stool seemed in between two examples
	d.	Because I did not have the time to make a decision
	e.	Other (Open ended question)
6.	If the	doctor wanted to know about your child's stool type, do you feel it would be
	helpfu	I to have an automatized tool to score the stool pictures for you?
	a.	Yes
	b.	No
7.	Would	d you say your child's stool pattern is, or was, a concern to you?
	a.	Yes, frequently
	b.	Yes, when my baby was younger
	c.	No, never
8.	Was it	easy to take the pictures of the diaper?
٠.		Yes
		No
		Why?

[figure not shown]
Protocol V2 12OCT2018

Protocol V2 120CT2018

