Questions 5, 6, and 7 of the Parental Satisfaction with ClaimIt Platform questionnaire pertain to the mother's perception of the usability of the stool scoring process. All of these questions are multiple choice and are thus recorded as categorical data. As such, frequencies and percentages of each answer choice will be given.

Question 5 includes logic to explain why a mother might have felt that scoring stool pictures was difficult. If she answers Yes, meaning she found some difficulty in scoring, she is given a list of choices by being asked "(If yes) Why?". One of these choices is an open-ended question whose answer will be recorded as free text. Answers to this option will be examined and listed as appropriate with any trends being highlighted as a frequency.

Endpoint 3: An assessment of mothers' perceptions of the usability of the ClaimIt app

Upon completing the observation period, each mother will be asked to complete the Parental Satisfaction with ClaimIt Platform questionnaire (Appendix I). Questions 1-4 and question 8 of this questionnaire pertain to the mother's perception of the usability of the ClaimIt app and will be analyzed as described below.

A mean overall ease of use score will be derived for Question 1 by averaging respondent's scaled answers. This score will be interpreted as the overall sentiment pertaining to the ClaimIt platform's ease of use for this trial. For example, a mean score of 4 would indicate that the sample of mothers for this study thought that ClaimIt was "easy" to use.

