Questions 2, 3, and 8 are Yes/No questions and, thus, their answers will be enumerated using frequencies and percentages of each answer choice. Questions 2, 3, and 8 all contain spaces for optional open-ended (free-text) responses, while Question 4 is a stand-alone open-ended question. All open-ended (free-text) responses will be listed for each question if the number of answers is reasonable enough to do so (e.g. <30 responses for a given question). Any trends found in the answers will be enumerated as a crude frequency. As nearly all answers to open-ended questions will be unique, all answers of a like theme will be recoded (for all intents and purposes) as the same category. For example, if one respondent answers question 4 ("Do you have any comments about using the application (favorable or unfavorable) that you would like the PIs to know?") by saying "I thought the app was easy to use", another answers "Easy to use", and another answers "Ease of use", then this answer will be recoded to "Easy to use" (for example) with a frequency of three (3). Any answers that are completely unique will be reported as such with a frequency of one (1).

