#### 9.2 Output Quality Checks

ObvioHealth follows a standard operating procedure for Quality Control of all study outputs. All results outputs produced for this study will be examined independently by at least two members of ObvioHealth's Biostatistics Department. All potential issues will be listed and resolved in a Quality Control meeting with the reviewing parties from OH Biostatistics and a member of the senior leadership team. The purpose of this meeting is to resolve any outstanding concerns with said output and ultimately approve all tables, listings, and figures, for insertion into the study's Clinical Study Report.

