# **13.** Appendices

## **Appendix I: Parental Satisfaction with ClaimIt Platform**

The following questions are regarding the use of the ClaimIt application during your participation in this clinical trial:

1. Please rate the ClaimIt application's overall ease of use on a scale of 1 to 5:

(Very Difficult) 1 2 3 4 5 (Very Easy)

- 2. Did the ClaimIt application malfunction?
  - a. Yes (will be asked a follow-up question)
  - b. No

If Yes, please describe what happened:

- 3. Have you participated in any other clinical study?
  - a. Yes (will be asked a follow-up question)
  - b. No

(*If yes*) What did you prefer about study participation using the ClaimIt application? Why?

(If yes) What did you prefer about participation in the previous study? Why?

4. Do you have any comments about using the application (favorable or unfavorable) that you would like the PIs to know?

\_\_\_\_\_ (Open ended question)

- 5. Did you find it difficult to score the stool pictures?
  - a. Yes
  - b. No

(If yes) Why?

- a. Because the app was not easy to use to see the example pictures
- Because it was not easy for me to score the stool, even with the example pictures provided
- c. Because sometimes the stool seemed in between two examples
- d. Because I did not have the time to make a decision
- e. Other \_\_\_\_\_\_ (Open ended question)
- 6. If the doctor wanted to know about your child's stool type, do you feel it would be helpful to have an automatized tool to score the stool pictures for you?
  - a. Yes
  - b. No
- 7. Would you say your child's stool pattern is, or was, a concern to you?
  - a. Yes, frequently
  - b. Yes, when my baby was younger
  - c. No, never

- 8. Was it easy to take the pictures of the diaper?
  - a. Yes
  - b. No

(if no) Why?\_\_\_\_\_

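### SAP 8.5.2 restricts the Question 8 free-text table (Table 2f) to mothers who answered Yes, but SAP Appendix I asks for a reason only after No

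*SAP*

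**What the plan says.** SAP 8.5.2 assigns Tables 2b to 2f to the free text from Questions 2, 3, 4, 5 and 8. For three of them it sets a population: "Tables 2b-c and 2f (Questions 2, 3, and 8, respectively) represent responses among subjects who answered" Yes.

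SAP Appendix I prints the questionnaire. In Questions 2 and 3 the affirmative option carries the note "Yes (will be asked a follow-up question", and the free-text prompt follows from it. Question 8 reads "Was it easy to take the pictures of the diaper", with Yes and No as options. Its request for a reason is printed with the condition that the answer was No.

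Protocol Appendix V has the same Question 8 ("easy to take the pictures of the diaper"), followed by a request for a reason with no visible condition.

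SAP 8.3 places Question 8 under the endpoint on usability of the app: "Questions 1-4 and question 8 of this questionnaire pertain to" that perception. It adds that "Questions 2, 3, and 8 all contain spaces for optional open-ended (free-text) responses" and that "All open-ended (free-text) responses will be listed for each question if the number of answers is reasonable enough to do so", giving fewer than 30 responses as an example. It puts no Yes or No restriction on any of these questions.

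**The concern.** Questions 2 and 3 ask about an event (a malfunction, an earlier study), so Yes is the answer that calls for detail. Question 8 asks whether a task was easy, so Yes is the favourable answer and the detail lies with No. Section 8.5.2 puts all three under one filter, probably because they were grouped in a single sentence.

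What is at stake is the informative part of Question 8. In a study whose product is a set of usable photographs, the reasons mothers give for finding the photography difficult are worth reporting, and SAP 8.3 plans to report them. A programmer who builds Table 2f from 8.5.2 would leave them out. The SAP does not say whether 8.3 or 8.5.2 takes precedence.

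**Working it through.** No arithmetic beyond a count applies, and the plan gives no figure to reproduce. The check compares each filter in SAP 8.5.2 with the branching in SAP Appendix I.

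| Table | Question | Filter in SAP 8.5.2 | Answer that opens the free text in SAP Appendix I | Match |
|---|---|---|---|---|
| 2b | 2 (malfunction) | Yes | Yes | yes |
| 2c | 3 (other clinical study) | Yes | Yes | yes |
| 2f | 8 (easy to take pictures) | Yes | No | **no** |

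Matches: 2 of 3. The one mismatch is Table 2f.

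**Reading 1, SAP Appendix I as printed.** Question 8 text exists only where the answer is No. Table 2f keeps only records where the answer is Yes. The intersection is empty, so there are 0 eligible responses and 0 reasons from mothers who answered No.

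**Reading 2, the reason was requested whatever the answer.** This is how Protocol Appendix V appears, but the answer letters are also lost there, so the condition may have dropped out when the PDF was read. Text would then exist after either answer, and the filter would keep only the Yes comments. Table 2f would not be empty, but it would still hold 0 reasons from mothers who answered No, and the omission would be harder to notice.

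Neither questionnaire ties the Question 8 reason to Yes. The contradiction rests on SAP 8.5.2 and SAP Appendix I alone; Reading 2 only shows that the filter is wrong on the other reading too.

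**Cross-check with SAP 8.3.** Listing all free text per question is compatible with Appendix I, although 8.3 names no trigger for Question 8 and so does not confirm one. It is not compatible with a filter that removes the No responses.

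No number of lost comments is projected. The documents give no expected share of No answers, and 8.3 calls the free text optional.

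**The case against.** The mismatch in the text is not in dispute. The strongest case on the other side is that little would follow from it.

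- **SAP 8.3 already commits to list the free text.** If it is followed, the reasons reach the report and only the label on Table 2f is wrong. This stands in part: the reasons are not certain to be lost. But 8.5.2 is the section that defines the tables, and 8.3 conflicts with it without overriding it.
- **The TLF Deliverable Shell sets the final tables.** SAP 8.5.1, 10.1 and 10.2 defer to it, and it may have the right population. It is not among the documents, so this can be neither confirmed nor assumed. It does limit what can be said about the table that would finally be produced.
- **The error would show itself.** SAP 8.5.2 has the tables list how many subjects completed the question or sub-question, and SAP 9.2 has outputs "examined independently by at least two members" of the biostatistics department. An empty Table 2f beside a non-zero No count in Table 2a might well be noticed. That is a reasonable safeguard under Reading 1 and a weaker one under Reading 2. A late check is no reason to leave a wrong rule in the plan.
- **Reading 2 may be an artefact of the PDF.** Agreed; the conclusion does not depend on it.

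**Conclusion.** The concern holds. The population that SAP 8.5.2 states for Table 2f is the opposite of the group that SAP Appendix I asks for text. Under the SAP's own form the table has 0 eligible responses; under either reading of the form it shows 0 reasons from mothers who answered No.

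The severity is minor. One descriptive table for an exploratory endpoint is affected. The No count is still given in Table 2a, and neither the image database nor the comparison of BITSS scores is touched. Confidence is high for the textual contradiction. It is lower for the effect on the final report, which depends on a shell that is not available and on which SAP section the programmer follows.

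A smaller wording point lies in the same section. Table 2a is described as Yes and No responses for a set of questions that includes Question 7, which has three choices. They can be collapsed to Yes and No, but SAP 8.3 already requires a frequency and percentage for every choice.

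**What to change.** In SAP 8.5.2:

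1. Keep the Yes filter for Tables 2b and 2c only.
2. Define Table 2f as the Question 8 free text among subjects who answered No, and show the number who answered No.
3. Confirm the wording of Question 8 as fielded in the app. If the reason was requested whatever the answer, list all Question 8 free text, split by Yes and No.
4. Bring the TLF Deliverable Shell into line.
5. While editing, state that Table 2a shows all three Question 7 choices, as 8.3 requires.

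The cost is one sentence on Table 2f, a few words on Table 2a, one check of the fielded questionnaire and the shell, and one filter in the table program. No new data are needed.

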#### 8.6 CONSORT diagram

Due to the 15% dropout rate built into the estimated total sample size, subjects whose study participation is terminated prematurely will not be replaced. The number and percentage of subjects who withdraw early will be presented in a CONSORT flow diagram equivalent; reasons for withdrawal will be presented in a table.

# 9 Quality Control

#### 9.1 Data Quality Checks

All raw data produced as part of this study will be examined by the ObvioHealth Biostatistics Department for plausibility prior to database lock. ObvioHealth and the sponsor's team will agree upon the final database as signified by a signed agreement.

#### 9.2 Output Quality Checks

ObvioHealth follows a standard operating procedure for Quality Control of all study outputs. All results outputs produced for this study will be examined independently by at least two members of ObvioHealth's Biostatistics Department. All potential issues will be listed and resolved in a Quality Control meeting with the reviewing parties from OH Biostatistics and a member of the senior leadership team. The purpose of this meeting is to resolve any outstanding concerns with said output and ultimately approve all tables, listings, and figures, for insertion into the study's Clinical Study Report.

# **10** Reporting

## **10.1 Clinical Study Report**

A Clinical Study Report will be developed and provided by ObvioHealth after the following have occurred: database lock, completed statistical analysis, and completed and client-approved TLF deliverable (through executed Tables, Listings, and Figures Deliverable Finalization Form). The report will review study background and methodology and will include relevant results, including tables, listings, and figures agreed upon in the TLF Deliverable Shell (see Section 10.2 immediately below).

#### **10.2 TLF Deliverable Shell**

In conjunction with the finalized SAP, ObvioHealth and Danone will agree upon a set of tables, figures, and listings that will be provided as part of the final study deliverable – the TLF Deliverable Shell.

The TLF Deliverable Shell will consist of a set of spreadsheets (or in other words, a workbook) that houses the empty versions of all tables and listings for this study. The final worksheet in this workbook will be a list of figures to be delivered. ObvioHealth and the sponsor will establish the final TLF Deliverable Shell by written agreement.

## **11 Study Limitations**

This is an exercise in collecting images for a database using the ClaimIt platform accompanied by a participant feedback questionnaire. As such, the study's ability to draw any statistical inferences is limited.

Inclusion criteria for this study may introduce biased sampling as participation is limited to subjects with access to reliable in-home internet and a mobile technology to accommodate the ClaimIt App. Furthermore, although the study instruments are based on a validated scoring tool, self-reported stool scores are subjective and not based on clinical evaluation. Finally, as the sample size was predetermined without a formal power calculation, the statistical evaluation was restricted to descriptive analyses with data visualizations of subjective measures and trends comparisons. However, this study provides proof of concept and utility of a digital clinical assessment.

# **13.** Appendices

## **Appendix I: Parental Satisfaction with ClaimIt Platform**

The following questions are regarding the use of the ClaimIt application during your participation in this clinical trial:

1. Please rate the ClaimIt application's overall ease of use on a scale of 1 to 5:

(Very Difficult) 1 2 3 4 5 (Very Easy)

- 2. Did the ClaimIt application malfunction?
  - a. Yes (will be asked a follow-up question)
  - b. No

If Yes, please describe what happened:

- 3. Have you participated in any other clinical study?
  - a. Yes (will be asked a follow-up question)
  - b. No

(*If yes*) What did you prefer about study participation using the ClaimIt application? Why?

(If yes) What did you prefer about participation in the previous study? Why?

4. Do you have any comments about using the application (favorable or unfavorable) that you would like the PIs to know?

\_\_\_\_\_ (Open ended question)

- 5. Did you find it difficult to score the stool pictures?
  - a. Yes
  - b. No

(If yes) Why?

- a. Because the app was not easy to use to see the example pictures
- Because it was not easy for me to score the stool, even with the example pictures provided
- c. Because sometimes the stool seemed in between two examples
- d. Because I did not have the time to make a decision
- e. Other \_\_\_\_\_\_ (Open ended question)
- 6. If the doctor wanted to know about your child's stool type, do you feel it would be helpful to have an automatized tool to score the stool pictures for you?
  - a. Yes
  - b. No
- 7. Would you say your child's stool pattern is, or was, a concern to you?
  - a. Yes, frequently
  - b. Yes, when my baby was younger
  - c. No, never

- 8. Was it easy to take the pictures of the diaper?
  - a. Yes
  - b. No

(if no) Why?\_\_\_\_\_

